#### **2.1.4.7 Gastrointestinal (GI) symptoms from the participant perspective**

The evolution of GI symptoms will be evaluated from the participant perspective using 3 PROMIS GI Symptom scales version 1.0 (nausea and vomiting, diarrhea, and belly pain) at Day 1, Weeks 1, 2, 3, 4, 5, 6, 7, 8, 12, 18, 30, 43, and 56.

### **2.1.5 Immunogenicity endpoints**

#### **2.1.5.1 Anti-drug (efpeglenatide) antibody**

Blood samples are taken to assess the Anti-drug antibody (ADA) status (positive/negative) and level (titer). Mapping the ADA epitopes of confirmed positive samples to different moieties of efpeglenatide, (ie, HMC001, exendin-4 and polyethylene glycol (PEG)) and cross-reactivity to endogenous GLP-1 (positive/negative), endogenous glucagon (positive/negative), neutralizing capacity of ADAs will also be evaluated for efpeglenatide groups in serum, at the time points specified in protocol.

Subjects with pre-existing ADAs are those with a positive ADA at Baseline. Non-missing post-Baseline titer values are deemed treatment-induced ADAs if the subject had a negative or missing ADA status at Baseline. Treatment-boosted ADAs are defined as a post-Baseline minimum 2-fold increase in Baseline titer value for subjects with pre-existing ADA at Baseline.

Persistent ADA response is defined as: Treatment-induced or treatment-boosted ADA detected at two or more sampling time points during the study (ie, including post-study observation period), where the first and last treatment-induced or treatment-boosted ADA samples (irrespective of any negative samples in between) are separated by at least 16 weeks.

Transient ADA response is defined as: (1) Treatment induced or treatment-boosted ADA detected only at 1 sampling time point during the study (excluding the last sampling time point); or (2) Treatment induced or treatment-boosted ADA detected at 2 or more sampling time points during the study, where the first and last treatment-induced or treatment-boosted ADA samples (irrespective of any negative samples in between) are separated by a period less than 16 weeks and the last time point is ADA-negative.

Indeterminate ADA response is defined as: (1) Only the last sampling time point is positive; or (2) the last two samples, separated by a period less than 16 weeks are positive.

The data will be presented as:

- Number of participants by ADA status (positive/negative) at scheduled visits
- Number of participants with treatment-induced ADAs among the participants with ADA negative or missing at Baseline
- Number of participants with treatment-boosted ADAs among the participants with ADA positive at Baseline
- ADA titer at scheduled visits
- Number of participants by ADA cross-reactivity to endogenous GLP-1 (positive/negative) at scheduled visits
- Number of participants by ADA cross-reactivity to endogenous glucagon (positive/negative) at scheduled visits
- Number of participants with ADAs directed against PEG linker of efpeglenatide at scheduled visits
- Number of participants with ADAs directed against the HMC001 moiety of efpeglenatide at scheduled visits
- Number of participants with ADAs directed against the exendin-4 moiety of efpeglenatide at scheduled visits
- Number of participants by status of anti-efpeglenatide neutralizing antibodies (positive/negative) at scheduled visits
  - Number of participants by status of neutralizing antibodies against endogenous GLP-1 (positive/negative) at scheduled visits

- Number of participants by status of neutralizing antibodies against endogenous glucagon (positive/negative)

### 2.1.6 Pharmacokinetic endpoints

Pharmacokinetic variables include the concentration of efpeglenatide in the efpeglenatide groups

- Serum concentration ( $C_{\text{trough}}$ ) of efpeglenatide at pre-dose (Weeks 4, 12, 24, 30)
- Serum concentration of efpeglenatide at least 1 additional postdose (3 days [ $\pm 1$  day] after administration of efpeglenatide, preferably between Week 8 and Week 12, but other weeks are also acceptable [eg, after 1st dose, 4th dose, or 12th dose]) in a subset of participants. All valid efpeglenatide samples collected will be sent to the laboratory to be analyzed, even if out of the specified window.

### 2.1.7 Pharmacodynamic/genomics endpoints

Pharmacodynamic parameters are not evaluated in this study.

## 2.2 DISPOSITION OF PARTICIPANTS

This section describes participants' disposition for both participant study status and the participant analysis populations.

Screened participants are defined as any participants who signed the informed consent form.

Randomized participants consist of all participants with a signed informed consent form who have had an open-label kit number allocated and recorded in the IRT database, regardless of whether the treatment kit was used or not.

The total number of participants in each of the following categories will be presented in the clinical study report using a flowchart diagram or summary table:

- Screened participants
- Screen failure participants and reasons for screen failure
- Nonrandomized but treated participants
- Randomized participants
- Randomized but not treated participants
- Randomized and treated participants
- Participants who have completed the 56-week study treatment period as per protocol
- Participants who did not complete the 56-week study treatment period, and main reasons for permanently treatment discontinuation
- Participants who completed the study as per protocol

- Participants who discontinued the study by main reasons for permanent study discontinuation
- Status at last study contact

For all categories of participants (except for the screened, screen failure, and nonrandomized but treated categories) percentages will be calculated using the number of randomized participants as the denominator. Reasons for treatment and study discontinuation will be supplied in tables giving numbers and percentages by treatment group. This summary will be provided by treatment group.

List of participants who discontinued treatment and/or study will be provided with reasons for discontinuation (including each specific reason categorized as 'OTHER'), including reasons related to COVID-19.

Kaplan-Meier cumulative incidence of early IMP withdrawal, premature discontinuation of treatment due to AE and study discontinuation will be provided.

Additionally, the following analysis populations will be summarized in a table by number of participants in the randomized population.

- Efficacy population: intent-to-treat (ITT) population, modified ITT (mITT) population
- Safety population
- ADA population
- Pharmacokinetics (PK) population

### **2.2.1 Protocol Deviations**

All significant deviations, potentially impacting efficacy analyses, randomization, and drug-dispensing irregularities, as well as other selected significant deviations will be summarized in tables giving numbers and percentages of deviations by treatment group in randomized population. Listing of participants with at least one significant deviation will be provided.

Additionally, participants with any protocol deviations due to COVID-19 will be summarized and listed separately.

## **2.3 ANALYSIS POPULATIONS**

Participants treated without being randomized will not be considered randomized and will not be included in any efficacy population.

The randomized population includes any participant who has been allocated to a randomized treatment regardless of whether the treatment kit was used or not.

For any participant randomized more than once, only the data associated with the first randomization will be used in any analysis population. The safety experience associated with any later randomization will be assessed separately.

The safety experience of participants treated and not randomized will be reported separately, and these participants will not be in the safety population.

### **2.3.1 Efficacy populations**

The efficacy analysis population will be the ITT population.

#### **2.3.1.1 Intent-to-treat population**

The ITT population is defined as all randomized participants, irrespective of compliance with the study protocol and procedures analyzed according to the treatment group allocated by randomization.

#### **2.3.1.2 Modified Intent-to-treat population**

Due to the study terminated early by sponsor on September 9, 2020 (hereinafter referred to as “early termination”), the efficacy analyses will be performed in mITT population instead of ITT population originally planned. The mITT population is defined as,

- Participants who have completed the study treatment, or
- Participants who discontinued the study treatment AND completed/discontinued the study before the early termination, or
- Participants who discontinued treatment before early termination and discontinued the study due to early termination within 30 days of the target Week 56 visit (Day 392), or
- Participants who discontinued treatment due to early termination within 30 days of the target Week 56 visit (Day 392).

Participants will not be included in mITT if they discontinued study due to termination and discontinued study treatment (before or due to early termination) and had visits performed more than 30 days before the target Week 56 visit (Day 392).

By-visit summary will be provided for ITT population in addition for mITT population.

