##### **Primary Analysis:**

The statistical analysis for the primary endpoint is described below.

The Baseline value is defined in [Section 2.1.1](#).

Analysis of the primary efficacy endpoint (change from Baseline to Week 56 in HbA1c) will be performed using the ITT population, using HbA1c measurements obtained during the study, including those obtained after IMP discontinuation or introduction of rescue therapy.

The primary efficacy endpoint of change in HbA1c from Baseline to Week 56 will be analyzed with missing values imputed by BOCF-like MI method for both efpeglenatide and dulaglutide groups, under the MNAR framework:

- For participants with missing HbA1c values at Week 56, the missing values will be imputed using a random draw from a normal distribution with mean equal to their Baseline HbA1c and the standard deviation equal to the pooled standard deviation calculated from the square root of the mean square error estimated from a regression model with Baseline HbA1c as the dependent variable and randomization strata and treatment as the covariates.

In this analysis, missing endpoint values will be imputed 10 000 times to generate 10 000 data sets with complete data. Each of the complete datasets after the imputation will be analyzed by the ANCOVA model with the treatment groups (efpeglenatide 4 or 6 mg, dulaglutide 1.5 mg), randomization stratum of screening HbA1c ( $<8.0$ ,  $\geq 8.0\%$ ), Visit 3 (Day 1) BMI ( $<30$  and

$\geq 30 \text{ kg/m}^2$ ), and geographical region (North America, Eastern Europe (including Hungary and Poland)) as fixed effects, and baseline HbA1c value as a covariate.

In case a baseline value needed for multiple imputations is missing, it will be imputed by the population mean at Baseline.

SAS pseudo-codes are provided in [Appendix A](#).

Results from each complete dataset will be combined to provide the adjusted mean change in HbA1c from baseline to Week 56 (regardless of treatment discontinuation or initiation of rescue therapy) for each treatment group, as well as the between-group difference (comparing each efpeglenatide group versus dulaglutide group) and the 95% CI for the difference. This will be implemented using MIANALYZE procedure in SAS. If the UB of the 2-sided 95% CI for the adjusted mean difference (efpeglenatide versus dulaglutide) in HbA1c change from baseline to Week 56 is  $\leq 0.3\%$ , the noninferiority will be declared.

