***Assessment of missing data:***

The availability of data (yes, no) at the endpoint visit (Week 56) will be summarized by treatment status (discontinued, completed) by treatment group.

Patients without data at the endpoint visit be summarized by treatment status (discontinued, completed) and by impact of Covid-19 on participants (yes, no) for each treatment group. Reasons for missing primary efficacy endpoint (ie, HbA1c at Week 56) will be listed.

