#### **2.4.4.2.1 HbA1c < 7.0 % at Week 56 (yes/no)**

Proportions of participants achieving the HbA1c target value of <7.0% at Week 56 will be compared between each efpeglenatide dose versus dulaglutide using a Cochran-Mantel-Haenszel (CMH) test stratified by randomization stratum of Screening HbA1c (<8.0, ≥8.0%) and Visit 3 (Baseline, Day 1) BMI (<30, ≥30 kg/m^2) in the ITT population. For categorial secondary endpoint in which HbA1c is assessed at Week 56, all HbA1c values at Week 56 will be used to determine whether a participant is a responder (HbA1c <7.0%) or not, even if they are measured after IMP discontinuation or introduction of rescue therapy. Participants with missing HbA1c data at Week 56 will be considered not achieving HbA1c < 7.0%. The nominal p-value from the CMH test will be presented. No rounding for HbA1c will be done.

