#### **2.4.4.2.2 Changes in FPG from Baseline to Week 56 and in body weight from baseline to Week 56**

Changes in FPG from baseline to Week 56 and in body weight to Week 56 will each be analyzed using the same ANCOVA model with missing values imputed by MI analysis method as the method used for the primary efficacy endpoint analysis. Differences between treatment groups and CIs will be estimated by this method. The least squares (LS) means, standard errors of LS means within each treatment group and the adjusted mean and associated two-sided 95% CI of the difference between efpeglenatide 4, 6 mg and 1.5 mg dulaglutide group will be presented.

Summary statistics at protocol scheduled visits and for the last on-treatment value will also be provided for FPG and body weight.

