### ***Efficacy data at Week 30 / Week 56***

The scheduled measurements at the endpoint visit (Week 30 or Week 56) as collected will be used in the efficacy analyses including those obtained after IMP discontinuation and/or introduction of rescue therapy. For participants whose efficacy measurement is not available at the endpoint visit, the measurement at unscheduled visit (including the end of treatment and/or study visit for those prematurely discontinued) will be used if the unscheduled measurement is within +/-30 days (7 days for FPG and SMPG) of the date of the end point visit [targeted study Day 210 for Week 30 (or Day 392 for Week 56)]. If multiple measurements are associated to the same targeted date, the closest to the targeted study day will be used. In case of equality, the last measurement will be used. If there are still no measurements for a given parameter at an endpoint visit, the data is considered missing for efficacy analyses, where multiple imputation would be applied as appropriately as described in [Section 2.4.4.1](#).

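### Among participants randomized too late for the Week 56 window, the mITT keeps only those who had already stopped treatment and left the study

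*SAP*

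**What the plan says.** SAP 2.3.1.2 states that, because of the termination, efficacy is analysed in the mITT instead of the ITT population. It gives four routes in:

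- Route 1: study treatment completed.
- Route 2: "Participants who discontinued the study treatment AND completed/discontinued the study before the early termination, or"
- Route 3: treatment stopped before termination, and study exit caused by termination within 30 days of Day 392.
- Route 4: "Participants who discontinued treatment due to early termination within 30 days of the target Week 56 visit (Day 392").

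The exclusion sentence begins "Participants will not be included in mITT if they discontinued study due to termination and discontinued study treatment" and applies when visits took place more than 30 days before Day 392. It covers only study exits caused by termination. No route mentions the randomization date. For the ITT population, the section promises only a by-visit summary.

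A missing Week 56 HbA1c is "imputed using a random draw from a normal distribution with mean equal to their Baseline HbA1c" (SAP 2.4.4.1, Primary Analysis). FPG and body weight have "missing values imputed by MI analysis method as the method used for the primary efficacy endpoint analysis" (2.4.4.2.2). For the responder endpoint: "Participants with missing HbA1c data at Week 56 will be considered not achieving HbA1c < 7.0"% (2.4.4.2.1). An off-schedule value can stand in for Week 56: it "will be used if the unscheduled measurement is within +/-30 days (7 days for FPG and SMPG") of the target day (2.5.4).

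On missingness, the SAP plans this: "The availability of data (yes, no) at the endpoint visit (Week 56) will be summarized by treatment status (discontinued, completed) by treatment group". SAP 2.2 tabulates reasons for discontinuation by arm. Neither splits participants by randomization date.

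**The concern.** A participant's randomization date is fixed before any outcome. Whether he or she later stops treatment and leaves is not. For participants who could not reach the Week 56 window, route 2 makes entry depend on the second. Contemporaries who stayed on treatment are dropped, and so are those who stopped but stayed in follow-up, as protocol 7.1 asks.

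Each late leaver adds a participant whose expected change is zero, or a non-responder, to the population that carries the noninferiority claim. If dropout is equal between arms, a true difference is diluted. That helps a noninferiority claim and hurts a superiority claim. If dropout is unequal, the extra weight on leavers works against the arm with more of them.

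**Working it through.** **Plan's own figure.** SAP 1.3 gives SD 1.1%, margin 0.3%, true difference 0, 300 per arm and power 91%. SE = 1.1 x sqrt(2/300) = 0.0898. Power = Phi(0.3/0.0898 - 1.96) = 91.6%, so the stated figure reproduces.

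**Who enters.** Putting each status through the four routes:

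| Status | No visit possible in Day 392 ± 30 | Stopping or exit visit inside the window |
|---|---|---|
| Completed treatment | not possible | in (route 1) |
| Stopped and left before termination | in (route 2) | in (route 2) |
| Stopped, still in follow-up at termination | out | in (route 3) |
| On treatment at termination | out | in (route 4) |

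In the left column, only the leavers are kept.

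**Dates, with Day 1 = randomization.** Lower window bound: 392 - 30 = Day 362. 9 September 2020 minus 361 days is 14 September 2019. For FPG the bound is 392 - 7 = Day 385, and 9 September 2020 minus 384 days is 22 August 2019.

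**Size.** The documents give no accrual dates, dropout rates or mITT size, so these inputs are assumptions:

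- L: share of each arm randomized late.
- p: dropout by Day 392, with no Week 56 value.
- m: fraction of p that a late participant has accumulated by termination. m is about 0.475 under a constant hazard with late follow-up uniform over 0-362 days; 0.7 is taken as an upper bound.

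The missing share in the mITT is s = [(1-L)p + Lmp] / [(1-L) + Lmp]. With L = 20%, p = 10% and m = 0.475: s = (0.08 + 0.0095)/(0.80 + 0.0095) = 11.06%, with 300 x 0.0095 = 2.9 late leavers per arm.

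Now set the difference in a cohort defined by date alone at 0.30, so that only the selection acts:

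- mITT difference D = 0.30(1-s)/(1-p) = 0.30 x 0.8894/0.90 = 0.2965
- n = 300 x 0.8095 = 243 per arm
- SE = 1.1 x sqrt(2/243) = 0.0998
- Type I error = Phi(-1.96 + (0.30 - D)/SE) = 2.71%
- Superiority power at a true advantage of 0.30 in the date cohort = Phi(D/SE - 1.96) = 84.4%, against 84.8% in the date cohort with n = 240

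At equal 10% dropout (m = 0.475 / m = 0.7):

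| Late share | Missing share, % | Late leavers per arm | Type I error, % | Superiority power, %: date cohort, then mITT |
|---|---|---|---|---|
| 10% | 10.5 / 10.7 | 1.4 / 2.1 | 2.60 / 2.65 | 88.7, then 88.5 / 88.4 |
| 20% | 11.1 / 11.5 | 2.9 / 4.2 | 2.71 / 2.82 | 84.8, then 84.4 / 84.2 |
| 30% | 11.8 / 12.6 | 4.3 / 6.3 | 2.85 / 3.02 | 79.8, then 79.0 / 78.6 |
| 50% | 14.1 / 15.9 | 7.1 / 10.5 | 3.21 / 3.59 | 65.6, then 63.6 / 62.7 |

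Over 5-20% dropout, type I error is 2.55-2.70% (m = 0.475) or 2.57-2.80% (m = 0.7) at 10% late. At 50% late it is 2.8-4.0% or 3.0-4.9%.

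**Unequal dropout.** Assume a change of -1.4% in those who stay. Added bias = 1.4 x [(s_high - s_low) - (p_high - p_low)]. For 10% v 15% dropout, 20% late and m = 0.475: 1.4 x [(0.1649 - 0.1106) - 0.05] = 0.006% HbA1c. Across 10 v 15% and 8 v 16%, and both values of m, it is 0.003-0.006 at 10% late, 0.006-0.014 at 20% and 0.02-0.05 at 50%. It always goes against the higher-dropout arm: conservative for noninferiority if that is efpeglenatide, anti-conservative if it is dulaglutide.

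**The case against.** Several points on the other side stand.

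- **Late entry by other routes.** A reader might infer that anyone short of Day 362 on 9 September 2020 enters only by leaving. The documents do not support that. Routes 3 and 4 run on when treatment or the study was stopped, and the exclusion runs on visit timing. Someone at Day 345 on that date who stops because of termination 20 days later, on Day 365, enters by route 4. The selection therefore applies only to those too late for any in-window stopping or close-out visit. The SAP does not give the length of the wind-down, so the late share is smaller than a count from 14 September 2019 would suggest.
- **Sensitivity analyses.** A reader might infer that every planned analysis carries the problem. The completer analysis contains no late leavers, though it has a selection of its own. The back-up method imputes from the arm's observed Week 56 data, which lessens the pull to baseline. Neither replaces the primary population.
- **FPG.** A reader might infer that everyone stopped between Day 362 and Day 384 lacks a usable FPG. SAP 2.5.4 also maps early-termination visits at or just before a scheduled visit onto that visit. How near counts as just before is not defined, so the inference is not established.
- **No late leaver is shown to exist.** Route 2 requires leaving the study as well as stopping treatment, and protocol 7.1 and 7.1.1 work against that. This limits the size but does not alter the rule.
- **Which population is primary is partly preference.** A date-defined cohort could instead be the sensitivity analysis. The argument for making it primary is that membership is then fixed at randomization.

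**Conclusion.** The definition has a real asymmetry: among participants beyond reach of the Week 56 window, it retains those who left and discards those who stayed. No table or by-visit summary would reveal it.

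The effect cannot be computed from the documents and is probably small. At equal 10% dropout, boundary type I error is about 2.6-2.8% with 10-20% late and 3.2-3.6% with half late. It becomes material only with a large late share, and the documents show none. All of this rests on assumed accrual, dropout and timing of dropout, an SD of 1.1% and, for unequal dropout, the assumed -1.4% change.

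The documents do not support reading this as evidence that the noninferiority conclusion is wrong. The SAP version dated 02-Oct-2020 follows the termination of a trial that is open-label for drug. That makes a population rule that does not depend on outcome worth having; it says nothing about intent. The point should be fixed because the repair is cheap.

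**What to change.** 1. For HbA1c, body weight and the responder endpoint, define the mITT by randomization date alone: everyone randomized on or before 14 September 2019, whatever their later treatment or study status, and no one randomized after it.
2. Keep the present definition as a sensitivity analysis, so that in-window close-out values from later-randomized participants are still used.
3. Report by arm the number of late participants who entered through route 2.
4. Treat FPG separately. Reconcile the early-termination mapping with the 7-day window, both in SAP 2.5.4. Run FPG restricted to those randomized on or before 22 August 2019 as a sensitivity analysis only, so that the hierarchy in 2.4.4.3 stays on one population.
5. Name the governing population consistently. SAP 2.3.1, 2.4.4, 2.4.4.1 (primary and subgroup analyses), 2.4.4.2.1 and the Appendix A dataset notes still say ITT, against 2.3.1.2.

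The cost is SAP wording and a date-based flag; no new data are needed. The downside is that a few observed in-window values from later-randomized participants leave the primary set and appear only in the sensitivity analysis.

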a In case of premature permanent IMP discontinuation, participants should have a visit as soon as possible after last IMP administration with the assessments normally planned for EOT visit (including a PK sample if the visit can be scheduled 7 days after the permanent IMP discontinuation). Afterwards, the participants should continue in the study up to the scheduled date of study completion and be followed up according to the study procedures as specified in the protocol. Every effort should be made to have the participant complete the Week 56 Visit assessments (primary and main secondary endpoints) as the minimum. For safety reasons, participants who do not want to continue to be followed in the study after IMP discontinuation, should be assessed 6 weeks (±1 week) from the last IMP dose (at the minimum) using the procedure normally planned for the post-treatment follow-up visit at EOS. At the time corresponding to their Week 56 Visit, all attempts will be made to contact the participants to inquire about safety/vital status.

Abbreviations: ADA: antidrug antibody, AE: adverse event, β-HCG: beta-human chorionic gonadotropin, BP: blood pressure, CV: cardiovascular, ECG: electrocardiogram, EOS: end of study, EOT: end of treatment, FPG: fasting plasma glucose, FSH: follicle-stimulating hormone, HbA1c: hemoglobin A1c, GI: gastrointestinal, HR: heart rate, IMP: investigational medicinal product, IRT: interactive response technology, PK: pharmacokinetics, PQATv2: Patient's Qualitative Assessment of Treatment version 2; PROMIS: Patient-Reported Outcomes Measurement Information System; R: Randomization; SAE: serious adverse event, SMPG: self-monitored plasma glucose, WOCBP: women of childbearing potential

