***Retrieved-dropout multiple imputation method:***

The retrieved-dropout multiple imputation sensitivity analysis will have 2 separate parts as follows:

1. Missing endpoint data in participants who prematurely discontinue the study treatment before the Week-56 visit will be imputed using a model built separately in each arm and estimated from participants in the same treatment arm who prematurely discontinue the study treatment before the Week-56 visit but have the measurement for the endpoint (retrieved dropouts). Considering that the number of participants in each treatment arm who discontinue the study treatment but have the measurement for the endpoint is expected to be small, a simple imputation model will be used, where only the Hb1Ac baseline measurements are included as the predictor. Each treatment group will have their own imputation model.
2. Missing endpoint data in all participants who stay on the study treatment until the Week-56 visit will be imputed using a model built separately in each arm and estimated from participants in the same treatment arm who stay on the study treatment until Week-56 visit and have the endpoint measurement, where randomization strata and Hb1Ac baseline measurements are included as the predictors.

In both parts, the missing data will be imputed using the regression method. After imputation, the completed data sets will be analyzed using an ANCOVA model similar to the primary analysis.

If there are no sufficient data to support the imputation approach in item 1 described above (less than 5 participants in any arms who prematurely discontinue the study treatment before the endpoint visit but have the measurement for the endpoint), a back-up method will be used. In particular, missing endpoint data in all participants, regardless of staying on the study treatment or not, will be imputed using a model built separately in each arm and estimated from participants in the same treatment arm with endpoint data, where randomization strata and corresponding baseline values are included as the predictors.

SAS pseudo-codes are provided in [Appendix A](#).

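### The mITT routes in SAP 2.3.1.2 have no place for participants who stopped treatment early and finished the study after the termination, so membership depends on treatment status

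*SAP*

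**What the plan says.** SAP 2.3.1.2 states that, because of the termination, "the efficacy analyses will be performed in mITT population instead of ITT population originally planned". It then lists four ways in:

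1. "Participants who have completed the study treatment, or" (no date is attached).
2. "Participants who discontinued the study treatment AND completed/discontinued the study before the early termination".
3. "Participants who discontinued treatment before early termination and discontinued the study due to early termination within 30 days of the target Week 56 visit".
4. Treatment stopped because of the termination, within 30 days of Day 392.

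One exclusion sentence follows. It removes people who left the study because of the termination, whose treatment had stopped before it or because of it, and whose visits were more than 30 days before Day 392. By-visit summaries are to be given for the ITT as well.

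Other sections bear on this. SAP 2.4.4, 2.4.4.1 and 2.5.4 all say that values measured after IMP discontinuation are used. Protocol 7.1.1 keeps people who stop IMP in the visit schedule to Week 56, and footnote a of Protocol 1.3 adds: "Every effort should be made to have the participant complete the Week 56 Visit assessments". SAP 2.3.1, 2.4.4 and 2.4.4.1 still name the ITT as the efficacy population.

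**The concern.** The inclusion routes and the exclusion sentence should between them place every randomized participant, and they do not. The people left unplaced are mostly those no longer on drug. Around the termination date a treatment completer is always in. An off-drug participant cut short by the termination near Day 392 is in under route 3. An off-drug participant who did what the protocol asks and finished the study is not.

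Stopping treatment happens after randomization and may differ between arms, here in a trial that is open-label for the drug. Selecting the population on it works against an analysis that is meant to count outcomes whether or not treatment continued. It would also set aside Week 56 values that sites were told to collect.

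**Working it through.** **1. The plan's own figure.** Inputs from SAP 1.3 and 2.4.4.1: 300 per arm, SD 1.1, margin 0.3, true difference 0, 1-sided alpha 0.025.

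SE = 1.1 × √(2/300) = 0.0898. Power = Φ(0.3/0.0898 − 1.96) = Φ(1.38) = 0.916. This agrees with the stated 91%.

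**2. Every status passed through SAP 2.3.1.2, read naturally.**

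| Treatment | Study | Route met | Named by exclusion sentence |
|---|---|---|---|
| Completed | any outcome, any date | 1 | no |
| Stopped before termination | completed or left before it | 2 | no |
| Stopped before termination | left because of it, within 30 days of Day 392 | 3 | no |
| Stopped before termination | left because of it, not within 30 days | none | yes |
| **Stopped before termination** | **completed after it** | **none** | **no** |
| **Stopped before termination** | **left after it for another reason** | **none** | **no** |
| Stopped because of termination, within 30 days | any | 4 | no |
| Stopped because of termination, not within 30 days | left because of it | none | yes |
| **Stopped because of termination, not within 30 days** | **completed, or left for another reason** | **none** | **no** |
| **Stopped after termination for another reason** | **any** | **none** | **no** |

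The bold rows are neither admitted nor excluded. None of them contains a treatment completer.

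**3. Can the main group exist?** Day 392 is Day 1 plus 391 days. It falls on or after 9 September 2020 for anyone with Day 1 on or after 15 August 2019. The documents give no enrolment dates, so the group is possible but not shown to be occupied.

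**4. Size, under assumptions.** Let a fraction f of an arm be lost, with mean HbA1c change g worse than in those kept. The mean of those kept equals the full mean minus f × g. The between-arm difference therefore moves by (f₁ − f₂) × g in absolute size.

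- 3% against 1%, g = 1.0: 0.02 × 1.0 = 0.02
- 5% against 2%, g = 1.0: 0.03 × 1.0 = 0.03
- 5% against 2%, g = 0.5: 0.03 × 0.5 = 0.015
- equal losses: 0

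For power, losing 3, 9 or 30 from 300 per arm gives 91.4%, 90.8% or 88.7%, against 91.6% with none lost. These start from the planned 300 per arm, which the termination itself will have reduced.

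**The case against.** **Route 2 can be read another way.** If the date condition attaches only to discontinuing the study, off-drug completers enter at any date. This is the less natural reading. It also leaves out off-drug participants who left after the termination for other reasons, so it narrows the gap without closing it. The SAP should not depend on it.

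**The ITT is still named elsewhere.** Under SAP 2.3.1, 2.4.4 and 2.4.4.1 as worded, these people are kept, and the ITT by-visit summaries keep them in any case. This stands: the point has effect only if 2.3.1.2 governs, as its own wording says it does.

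**Nothing shows that anyone is affected.** This also stands. A reader might infer that measured Week 56 values have been discarded, or that the sponsor meant to remove off-drug participants. The documents support neither. They do not say how many people completed after 9 September, or whether dosing or follow-up continued after it. The exclusion sentence does not mention this group, so an oversight in drafting is the simpler explanation.

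**The follow-up visit.** A reader might also infer that everyone off drug with Week 56 before 9 September and the final visit after it is caught. Protocol 1.1 and 1.3 set that visit at six weeks after the last dose, not after Week 56. It falls after Day 392 only when the last dose was within 42 days of Day 392.

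**The retrieved-dropout imputation.** It is tempting to say that the loss pushes this sensitivity analysis to its back-up method, which applies with "less than 5 participants in any arms who prematurely discontinue the study treatment before the endpoint visit but have the measurement for the endpoint". What matters is the number remaining. If 10% to 15% of 300 were off drug but followed, that is 30 to 45 per arm, and losing 15% of 30 leaves 25.5. With a 15% loss, an arm falls below 5 only if it started with fewer than 5/0.85 = 5.9. The Appendix A code notes also describe the input to that imputation as the ITT.

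**Conclusion.** As written, SAP 2.3.1.2 does not partition the randomized participants, and on the natural reading the people it leaves out are separated from those it keeps by treatment status. That conflicts with the plan to use HbA1c obtained off drug. The main gap is the participant who stopped IMP before 9 September 2020 and completed the study after it. The same gap covers off-drug participants who left after the termination for other reasons, and any who stopped treatment after it for a reason other than the termination.

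The likely effect is small: 0.02 to 0.03 points in the unequal-loss illustrations with g = 1.0, or at most a tenth of the margin, and nothing if losses are equal. The loss fractions and the outcome gap are assumptions, and the documents support no direction. The rule should be corrected because it is inconsistent and easily fixed, not because it is shown to change the conclusion.

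**What to change.** Make the exclusion sentence the definition. The mITT would be all randomized participants except those who left the study because of the early termination and whose last visit was more than 30 days before Day 392. State that this holds whenever and for whatever reason treatment stopped, and whether or not a Week 56 value was observed. Other missing Week 56 values are then imputed as already planned. Align SAP 2.3.1, 2.4.4 and 2.4.4.1 with this population, and say how study completion is dated for someone who stopped IMP early.

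An alternative is to add a route for anyone with a Week 56 value or who completed the study. That would select on having been observed, and would still leave out off-drug participants who left after the termination without a value, whom the primary analysis is built to impute.

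The cost is a minor rewording and a few more participants with imputed values. No new data are needed.
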